APPENDIX 2 STRONG AND MODERATE CYP3A INHIBITORS AND INDUCERS

	Strong	Moderate
3A Inducers	Avasimibe, carbamazepine, phenytoin, rifampin, St. John's wort	Bosentan, efavirenz, etravirine, modafinil, nafcillin
3A Inhibitors	Boceprevir, clarithromycin, conivaptan, grapefruit juice, indinavir, itraconazole, ketoconazole, lopinavir/ritonavir, mibefradil, nefazodone, nelfinavir, posaconazole, ritonavir, saquinavir, telaprevir, telithromycin, voriconazole	Amprenavir, aprepitant, atazanavir, ciprofloxacin, darunavir/ritonavir, diltiazem, erythromycin, fluconazole, fosamprenavir, Seville orange juice, grapefruit juice, imatinib, verapamil

From: [Drug Development and Drug Interactions: Table of Substrates, Inhibitors and Inducers. U.S. Food and Drug Administration.](#)

**APPENDIX 3 SENSITIVE CYP3A SUBSTRATES INCLUDING THOSE WITH
NARROW THERAPEUTIC INDEX**

3A Sensitive Substrate	Subset with Narrow Therapeutic Index
Alfentanil, aprepitant, budesonide, buspirone, conivaptan, darifenacin, darunavir, dasatinib, dronedarone, eletriptan, eplerenone, everolimus, felodipine, indinavir, fluticasone, lopinavir, lovastatin, lurasidone, maraviroc, midazolam, nisoldipine, quetiapine, saquinavir, sildenafil, simvastatin, sirolimus, tolvaptan, tipranavir, triazolam, vardenafil	Alfentanil, astemizole, cisapride, cyclosporine, dihydroergotamine, ergotamine, fentanyl, pimozone, quinidine, sirolimus, tacrolimus, terfenadine

From: [Drug Development and Drug Interactions: Table of Substrates, Inhibitors and Inducers. U.S. Food and Drug Administration.](#)

APPENDIX 4 SCHEDULE OF ASSESSMENTS

PART A: 12-WEEK TREATMENT/ 12-WEEK FOLLOW-UP:

	Screen	Day 1, Week 1 Pre-dose	Day 1 Week 1 Post-dose ^e	Day 2, Week 1 ^a	Day 15, Week 3 +/- 3 days	Day 29, Week 5 +/- 3 days	Day 57, Week 9 +/- 7 days	Day 85, Week 13 +/- 7 days	Day 113, Week 17 +/- 7 days	Day 141, Week 21 +/- 7 days	Day 169, Week 25 +/- 7 days	Unscheduled Visit
Informed Consent	X											
Inclusion/Exclusion Criteria	X	X										
Height	X											
Weight	X	X			X	X	X	X	X	X	X	X
Physical exam./med. History, PDAI and ABSIS	X											
Abbreviated physical exam, PDAI, ABSIS		X			X	X	X	X	X	X	X	X
ECG (12-lead)	X											(X) ^b
Vital Signs	X	X		X	X	X	X	X	X	X	X	X
Urinalysis	X											
Hep B & C, HIV, T-spot TB Test, QuantiFERON®-TB Gold, QuantiFERON®-TB Gold Plus (QFT Plus)	X											
Pregnancy test ^c	X	X				X	X	X			X	
Skin biopsy ^d	X											
Hem, Coag, Chem	X ^e	X			X	X	X	X				X
FSH ^f	X											
BTK occupancy sample		X ^g	X ^h	X	X	X	X	X				(X) ^b
PK sample		X	X ^h	X	X	X	X	X				(X) ^b
Anti-DSG antibodies		X				X	X	X	X	X	X	
Photography (Optional) ⁱ		X			X	X	X	X	X	X	X	X
ABQOL & TABQOL		X			X	X	X	X	X	X	X	X
SNAQ questionnaire		X			X	X	X	X	X	X	X	X
AEs		X		X	X	X	X	X	X	X	X	X
Concomitant Medications	X	X		X	X	X	X	X	X	X	X	X
Drug dispensed		X				X	X					
Drug reconciliation					X	X	X	X				

Schedule of Assessments Footnotes:

- a. Withhold PRN1008 on morning of Day 2 until PK/PD measurement has been taken as close to 12 hours after second dose as possible. Where follow-up on Day 2 is not possible, PK/PD samples may be taken on another day in the first week of treatment. On all other days, instruct patient to take PRN1008 in the morning as usual prior to clinic and take note of the time taken. Extra PK/PD sample intended for 1 to 5 days after dose adjustment or to replace missing samples—not required for other extra visits.
- b. Only if clinically indicated.
- c. For women of childbearing potential only. Serum pregnancy test done at screening, urine dip test done at other time points.
- d. Performed only if no suitable prior biopsy.
- e. TSH and CPK taken as part of chemistry panel.
- f. To confirm postmenopausal status for women who are not surgically sterile only.
- g. Two-8mL pre-dose blood tubes to be collected at baseline to ensure sufficient samples for later time point assay calculations.
- h. 2 hours post-dose (+/- 15 mins)
- i. Photography is used to document skin disease changes; ideally in most patients. Strict masking of patient identity is required.

[figure not shown]
PART B: SCHEDULE OF ASSESSMENTS (24-weeks Treatment/ 4-weeks Follow Up)

[figure not shown]
	Screen	Day 1, Week 1 Pre-dose	Day 1 Week 1 Post-dose ^a	Day 2, Week 1 ^g	Day 15, Week 3 +/-3 days	Day 29, Week 5 +/-3 days	Day 57, Week 9 +/-7 days	Day 85, Week 13 +/-7 days	Day 113, Week 17 +/-7 days	Day 141, Week 21 +/-7 days	Day 169, Week 25 +/-7 days	Day 197, Week 29 +/-7 days	Unscheduled Visit
Informed Consent ^k	X												
Inclusion/Exclusion Criteria	X	X											
Height	X												
Weight	X	X			X	X	X	X	X	X	X	X	X
Physical exam/med.History PDAI, ABSIS	X												
Abbreviated physical exam., PDAI, ABSIS		X			X	X	X	X	X	X	X	X	X
ECG (12-lead)	X												(X) ^b
Vital Signs ^j	X	X		X	X	X	X	X	X	X	X	X	X
Urinalysis	X												
Hep B & C, HIV, T-spot TB Test, QuantiFERON®-TB Gold, QuantiFERON®- TB Gold Plus (QFT Plus)	X												
Pregnancy test ^c	X	X				X	X	X	X	X	X	X	
Skin biopsy ^d	X												
Hem, Coag, Chem	X ^e	X			X	X	X	X	X	X	X	X	X
FSH ^f	X												
BTK occupancy sample		X ^g	X ^h	X	X	X	X	X	X	X	X	X	(X) ^b
PK sample		X	X ^h	X ^a	X	X	X	X	X	X	X	X	(X) ^b
Anti-DSG antibodies		X				X	X	X	X	X	X	X	
Photography (Optional) ⁱ		X			X	X	X	X	X	X	X	X	X
ABQOL & TABQOL		X			X	X	X	X	X	X	X	X	X
SNAQ questionnaire		X			X	X	X	X	X	X	X	X	X
AEs		X		X	X	X	X	X	X	X	X	X	X
Concomitant Medications	X	X		X	X	X	X	X	X	X	X	X	X
Drug dispensed		X				X	X	X	X	X			
Drug reconciliation					X	X	X	X	X	X	X	X	

[figure not shown]
Schedule of Assessments Footnotes:

- a. Withhold PRN1008 on morning of Day 2 until PK/PD measurement has been taken as close to 12 hours (when *bid* dosing) or 24 hours (when *qd* dosing) after the prior dose as possible. Where follow-up on Day 2 is not possible, PK/PD samples may be taken on another day in the first week of treatment. On all other days, instruct patient to take PRN1008 in the morning as usual prior to clinic and take note of the time taken. Extra PK/PD sample intended for 1 to 5 days after dose adjustment or to replace missing samples—not required for other extra visits.
- b. Only if clinically indicated.
- c. For women of childbearing potential only. Serum pregnancy test done at screening, urine dip test done at other time points.
- d. Performed only if no suitable prior biopsy.
- e. TSH and CPK taken as part of chemistry panel.
- f. To confirm postmenopausal status for women who are not surgically sterile only.
- g. Two-8mL pre-dose blood tubes to be collected at baseline to ensure sufficient samples for later time point assay calculations.
- h. 2 hours post-dose (+/- 15 mins)
- i. Photography is used to document skin disease changes; ideally in most patients. Strict masking of patient identity is required.
- j. Vital sign include blood pressure (BP), pulse rate, body temperature and respiratory rate and are recorded at the time points specified
- k. The Schedule of Assessments has been revised to be consistent with the 24 week treatment duration and 4 week safety follow up assessments described in this protocol Version 5, Part B. Patients enrolled in an earlier protocol version (Part A) who are in the active 12-week treatment period are eligible to continue treatment, initially at their current dose, for up to a total of 24 weeks active treatment upon review and signature of the Part B EC approved Patient Informed Consent Form, with procedures and tests per this Schedule. Patients that have completed **Part A** of the trial are also eligible to be screened as a **Part B** patient, upon review and signature of the *Part B* EC-approved Patient Informed Consent Form.

[figure not shown]
**APPENDIX 5 PEMPHIGUS DISEASE ACTIVITY AND QUALITY OF LIFE
EVALUATION INSTRUMENTS: ABQOL, TABQOL, PDAI, ABSIS**

[figure not shown]

[figure not shown]
Treatment of Autoimmune Bullous Diseases Quality of Life Assessment (TABQOL)

[figure not shown]

From: [Tjokrowidjaja et al. 2013](#)

[figure not shown]
Pemphigus Disease Activity Index (PDAI) ([Murrell et al. 2008](#))

Autoimmune Bullous Skin Disorder Intensity Score (ABSIS) ([Rosenbach et al. 2009](#))

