Following single and multiple oral doses of PRN1008 in Study PRN1008-001, mean BTK occupancy in PBMCs of more than 70% was observed 4 hours or later following doses of 300 mg or more on Day 1. Figure 1 shows clinically effective levels of BTK occupancy with a 300 mg bid dose on Day 1, with slightly reduced interpatient variability, and slightly higher Hour-4 values, observed after multiple days of dosing. Three subjects with BTK occupancies at 12 hours on Day 1 in the 40% range all had 12-hour occupancies above 60% by Day 10.

Figure 1 Individual and Mean BTK Occupancy Data from HV Study PRN1008-001 with the Liquid Formulation of PRN1008*

*Tablet equivalent doses are 428 mg twice daily after correction for relative bioavailability of ~70%.
 A second dose was not administered on Day 10.

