1.5.2 Pharmacokinetics and BTK Occupancy in Pemphigus Patients

In this Study PRN1008-005, PK sampling is being conducted in all patients for population PK analysis. Blood samples were drawn pre-dose and at 2 hours following PRN1008 administration on the first day of therapy, pre-dose on the second and seventh day of therapy, and then at random times following dosing at other study visits. Preliminary data suggest that plasma concentrations at 2 hours, steady state 2 hours, and pre-dose were generally consistent to those seen in Phase 1 studies, as corrected for formulation ([Figure 4](#)).

Figure 4 **Distribution of Plasma Concentrations at BTK Occupancy Timepoints**

[figure not shown]

BTK = Bruton's tyrosine kinase; SS = steady state

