1.5.3 BTK Occupancy in Patients with Pemphigus

Target occupancies, based on efficacy in animals and the levels reached with a liquid formulation dose of 300 mg *q12h*, were approximately 80% on Day 1, approximately 70% on Day 2 pre-dose (indicated as SS 12 hr), and approximately 90% at SS 2 hr (Figure 5). Thus, target occupancy levels are being reached in nearly all individuals with a 400 mg twice daily dose.

Figure 5 BTK Occupancies (Mean and Standard Deviation) Based on Approximate Timepoints Following Dosing

BTK = Bruton's tyrosine kinase; SS = steady state

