2 RATIONALE AND JUSTIFICATION FOR THE STUDY AND THE STUDY DESIGN

2.1 Rationale for the Study Design

This open-label, pilot study is designed to explore the initial efficacy and safety of PRN1008 in PV and to enable the accurate design of pivotal randomized clinical trials which are to follow. An open-label design was chosen for several reasons: PV does not spontaneously remit so there is no placebo effect to account for; clinicians need to know when to use rescue corticosteroids, if necessary, in a timely manner; and lastly, the pilot nature of the investigation itself is best explored in an open-label fashion.

Because of the ability to guide individualized dosing with BTK occupancy measurement, the use of which has been validated in a naturally occurring canine pemphigus study, this assay was used to supplement the clinical response assessments in making dose-adjustments in **Part A**. More than 95% of patients in **Part A** (20/21) had adequate BTK occupancies (mean 86% pre dose at steady-state). In **Part B**, the clinical efficacy of the 400 mg qd dose is being explored to see if lower BTK occupancies will still equate to clinical efficacy. For this reason, clinical response alone, and not BTK occupancies, is recommended to guide dose adjustment in **Part B**.

Given the efficacy seen in this pemphigus study to date at varied clinical severities, and the updated, supporting, chronic, GLP toxicology ([Section 1.3](#)), there is clinical equipoise to study PRN1008 monotherapy (or with low dose CS) in patients with mild-to-severe (baseline PDAI 8-60), corticosteroid-naïve or relapsing PV, with close observation and appropriate corticosteroid rescue protocols.

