2.2 Selection of the Starting Clinical Dose of PRN1008 in Pemphigus

400 mg bid (Part A): The 400 mg *bid* starting dose is based upon the dose known to produce ~70% BTK occupancy at trough (~85% average occupancy over the day), as adjusted by results of the relative bioavailability study, where the tablet had ~70% of the exposure of the equal dose of the liquid formulation. Adequate BTK occupancies with 400 mg bid dosing of the IR tablet has been confirmed in nearly all of the 21 patients with pemphigus studied to date. To confirm achievement of target, BTK occupancy measurements after the first dose will be expeditiously processed and provided to the treating physician in time for a follow-up visit at Day 15 (**Part A** only). This dose level has adequate safety factors to exposures in chronic toxicology studies ([Section 1.3](#)).

400 mg qd (Part B): In some but not all animal studies, a dose-response relationship between pre-dose BTK occupancy and clinical efficacy was observed. As it is unknown whether a once daily PRN1008 dose will provide adequate pharmacodynamics effect, a 400 mg qd dose is being tested in **Part B**, with the option to expeditiously dose-escalate to higher doses at or after the Week 3 visit. This dose level has adequate safety factors to exposures in chronic toxicology studies ([Section 1.3](#)).

Please refer to [Investigator Brochure](#), Section 5.5.3, for additional information.

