8.2 Laboratory Assessments Part A and B

Note: Laboratory assessments will be performed at both central and local laboratories, if required.

- **Hematology**: hemoglobin, hematocrit, erythrocyte count (RBCs), thrombocyte count (platelets), leukocyte count (WBCs) with differential in absolute counts (including neutrophils, eosinophils, basophils, lymphocytes, and monocytes)
- **Coagulation**: PT/INR, thrombin time, aPTT, fibrinogen level.
- **Serum Chemistry**: Aspartate aminotransferase (AST), Alanine aminotransferase (ALT), Total, direct, and indirect bilirubin levels, Alkaline phosphatase (ALP), Albumin, Creatinine, Urea, Total Protein, Sodium, Chloride, Calcium, Phosphate, Potassium, Glucose (random), creatine phosphokinase (CPK) and thyroid stimulating hormone (TSH)
- **PK**: Plasma PRN1008 concentration
- **PD**:
 - BTK occupancy in PBMCs at baseline (pre-dose), and 2 and 24 hours after the first dose, then at various times of the day during follow-up visits. For the Day 2 (24 hour) BTK occupancy, PRN1008 should be taken as usual in the evening (only if *bid* dosing) and the PRN1008 morning dose withheld in order to take the blood sample approximately 12 hours after the prior evening dose (for *bid* dosing) or 24 hours after the last dose (for *qd* dosing). Where follow-up is not feasible on Day 2, another day in the first week

of therapy may be used to get trough occupancy instead. For all other visits, occupancy is measured at random times after the usual morning dose.

- Anti-desmoglein-1 and -3 autoantibody titers by enzyme-linked immunosorbent assay (ELISA)
- **Urinalysis:** pH, specific gravity, protein, glucose, ketones, bilirubin, blood, nitrites, urobilinogen and leukocytes measured by dipstick
- **Serology:** HIV, Hepatitis B and Hepatitis C and T-spot TB Test or QuantiFERON® TB testing or QuantiFERON®-TB Gold Plus (QFT Plus) at screening only
- **Pregnancy or FSH:** Serum pregnancy test for women of child bearing potential or serum FSH for post-menopausal females

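### Part B tests whether lower BTK occupancy on 400 mg qd is enough, but no steady-state qd trough is systematically scheduled

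*Protocol*

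**What the plan says.** Protocol Section 2.1 gives the purpose of the qd start: "the clinical efficacy of the 400 mg qd dose is being explored to see if lower BTK occupancies will still equate to clinical efficacy". Section 2.2 supports it with the remark that, in some but not all animal studies, "a dose-response relationship between pre-dose BTK occupancy and clinical efficacy was observed", and says it is not known whether once-daily dosing has an adequate pharmacodynamic effect.

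The sampling rule appears in the Synopsis (Study Design), Section 8.2, Appendix 4 (Part B, footnote a), and Part B SAP Section 2.2 and Table 1. The morning dose is withheld for a trough on Day 2, or on another day of the first week if Day 2 cannot be done. After that, footnote a says "On all other days, instruct patient to take PRN1008 in the morning as usual prior to clinic and take note of the time taken", and Section 8.2 says "For all other visits, occupancy is measured at random times after the usual morning dose".

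Three other texts describe troughs differently:
- Section 1.5.2 reports samples taken "pre-dose on the second and seventh day of therapy, and then at random times following dosing at other study visits". Neither Appendix 4 schedule contains a seventh-day pre-dose sample.
- Section 1.5.3 gives one occupancy target as "approximately 70% on Day 2 pre-dose (indicated as SS 12 hr", which puts a steady-state label on a Day 2 sample.
- Appendix 1A (Part A rescue, Criteria #2 and #3) relies on the patient's latest trough occupancy well after week 1.

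**The concern.** Efficacy is judged from Week 5 to Week 25, when patients have been dosed for weeks. If the trough set against it comes from the first dose, and occupancy builds up afterwards, the occupancy recorded for responders is lower than the occupancy at which they responded. An occupancy-response reading would then lean towards finding that low occupancy is enough, and the protocol intends these results to guide later trials.

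The comparison with Part A has a similar weakness. Section 2.1 gives the Part A mean as 86% pre-dose at steady state. The Part A Day 2 sample follows the second dose by about 12 h, whereas the Part B qd Day 2 sample follows the first dose by about 24 h. Part B would tend to look lower partly because of when it was sampled.

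**Working it through.** The plan states no figure to reproduce here, so the check has two parts.

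**1. What is sampled in a Part B patient on qd**

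| Visit | Morning dose | Sample | qd doses already taken |
|---|---|---|---|
| Day 2 | withheld | about 24 h after dose | 1 |
| Days 3 to 7 (only if Day 2 is not possible) | withheld | about 24 h after dose | 2 to 6 |
| Days 15 to 169 | taken before clinic | random time after dose | many |
| Extra samples (after a dose change, or replacing a missing one) | no instruction to withhold | not fixed | varies |

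Day 169 is no exception, since the Synopsis has the final dose taken that morning. Patients who respond and stay on qd have no dose change, and so no extra sample on that ground. The late part of the 24 h interval has no planned observation after week 1.

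**2. Can Day 2 stand in for steady state?**

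*Direct evidence.* Section 1.4.1: "Three subjects with BTK occupancies at 12 hours on Day 1 in the 40% range all had 12-hour occupancies above 60% by Day 10". The rise is at least 10 to 20 points (60 − 50 and 60 − 40), at 12 h, apparently on the 300 mg bid liquid dosing that Figure 1 describes.

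*Plasma accumulation.* R = 1/(1 − 2^(−τ/t½)), with inputs from Section 1.5.1.
- t½ = 3 to 4 h: R = 1.07 to 1.14 on bid (τ = 12 h) and 1.00 to 1.02 on qd (τ = 24 h). On this input the Day 2 plasma trough is already near steady state.
- The same section reports R = 1.8 on bid. Then 2^(−12/t½) = 1 − 1/1.8 = 0.444, so the effective t½ is 10.3 h. If that carries over to qd (an assumption), 2^(−24/t½) = 0.444² = 0.198 and R = 1/(1 − 0.198) = 1.25. The Day 2 trough is then 80% of steady state. After 2 doses it is 96%, and after 3 doses 99%.

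The protocol's two plasma figures therefore give different answers.

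*Occupancy, illustrative only.* Suppose each dose binds a share e of free BTK, and a share d of bound BTK is still bound at 24 h. The Day 2 trough is d·e. The steady-state trough is d·e/(1 − r), with r = d(1 − e), and the gap after k doses is the steady-state value times r^k. Neither e nor d is in the documents; e = 0.6 to 0.8 and d = 0.3 to 0.85 are assumed.
- Smallest gap (e = 0.8, d = 0.3): Day 2 is 24.0%, steady state 25.5%, gap 1.5 points.
- Largest gap (e = 0.6, d = 0.85): Day 2 is 51.0%, steady state 77.3%, gap 26.3 points. After 6 doses (Day 7) the gap is 77.3 × 0.34^6, about 0.1 point.

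A Day 2 qd trough may therefore be close to steady state or well below it. A trough late in week 1, or on Day 15, would be at steady state under this model.

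**The case against.** **The schedule delivers the stated outcome measure.** Section 11.3.2 asks for occupancy at 2 and 24 h after the first dose and at varied later times. No objective names a steady-state trough, and the pre-dose relation in Section 2.2 is limited to some animal studies. This stands. The point is that the outcome measure does not fully serve the purpose stated in Section 2.1; it is not that an endpoint goes uncollected.

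**A reader might infer that a steady-state qd trough is never measured.** That goes too far. The first-week fallback permits a trough after several qd doses. It is conditional, though, and it puts first-dose and multi-dose troughs under one visit label.

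**A reader might infer that the Part A rescue rules can only ever use a first-week trough, or that patients will be misclassified against the 50% cut.** Neither is supported. Appendix 1A, Criteria #2, provides for a new trough draw when none is available. The cut belongs to Part A: Part B adjusts dose on clinical response, and Appendix 1B has no occupancy threshold.

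**The volunteer evidence is thin.** It is three subjects singled out for low Day 1 values, so part of their rise may be regression to the mean. The same paragraph calls the general multiple-dose change slight, and Section 2.1 reports adequate occupancy in 20 of 21 Part A patients. This limits any claim about size. It does not show that Day 2 on qd represents steady state.

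**The analysis plan is elsewhere.** The Part B SAP (Sections 4.5 and 4.6) sends BTK and PK/PD analyses to separate SAPs that are not available here. Dose times are recorded, and a model could use the random-time samples. So it cannot be said that efficacy will be paired with a first-dose trough. A model would still be extrapolating into an interval with no planned observation after week 1.

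**Conclusion.** The concern holds in this form: Part B has no systematically scheduled steady-state qd trough, so its stated occupancy question lacks the direct measurement it most needs. A first-day trough can understate later occupancy; by how much on qd is unknown. The range of 1.5 to 26 points rests entirely on assumed binding and retention shares and should be read as showing that the gap could be negligible or material. If there is a gap, using Day 2 as the trough pushes towards concluding that low occupancy suffices.

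The Part A comparator is also uncertain. Section 2.1 does not say which sample gave 86%, and Section 1.5.3 labels Day 2 as steady state, so that value may itself come from the first week.

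The primary efficacy endpoint and Part B dose decisions do not use occupancy and are unaffected. This is a worthwhile, inexpensive improvement to the pharmacodynamic part of a descriptive pilot.

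**What to change.** 1. In footnote a of the Part B schedule, have the Day 15 BTK/PK sample drawn before that morning's dose, using the Day 2 procedure and before any escalation at that visit. Make the same edit in the Synopsis, Section 8.2, and Part B SAP Section 2.2 and Table 1.
2. In the BTK and PK/PD SAPs, use this value as the steady-state qd trough for patients still on 400 mg qd. Identify separately those who entered Part B on a higher dose, and those whose dose was raised earlier under Appendix 1B, Criteria #2.
3. Label Day 2 a first-dose trough and analyse Days 3 to 7 replacement samples separately.
4. Reconcile the seventh-day sample in Section 1.5.2, the Day 2 label in Section 1.5.3 and the latest-trough wording in Appendix 1A with what the schedule collects, and state which sample gave the 86%.

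Day 15 is preferable to Day 29, because Table 3 allows escalation from the Week 3 visit. A Day 29 sample would mix qd and bid troughs and leave qd values mainly in responders.

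Cost: a repeated footnote edit and a line in each separate SAP, with no added visit or tube. One random-time sample per patient becomes a trough, and the Day 15 visit must fall about 24 h after the previous dose. If Part B sampling is already complete, items 2 (as a stated limitation), 3 and 4 can still be done.
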